3. STUDY DESIGN

[figure not shown]
3.1 DESCRIPTION OF THE STUDY

Study MO39171 is a phase III/IV, single-arm, multicenter study of the long-term safety and efficacy of atezolizumab treatment in patients with Stage IIIb or Stage IV NSCLC who have progressed following standard systemic chemotherapy (including if given in combination with anti-PD-1 therapy, after anti-PD-1 as monotherapy, or after TKI therapy). Patients with a previously detected sensitizing EGFR mutation or ALK fusion oncogene must have received targeted therapy (TKI) followed by at least one line of standard systemic chemotherapy prior to receiving atezolizumab. Overall, patients should not have received more than two lines of standard systemic chemotherapy. Patients will also be eligible if they discontinued first-line or second-line therapy due to intolerance.

The study will consist of a Screening Period (Day –28 to Day –1), a Treatment Period, a Treatment Discontinuation Visit occurring \leq 30 days after the last dose of study medication, and a Follow-Up Period. Day 1 (baseline) will be defined as the first day the patient receives atezolizumab. It is anticipated that the trial will enroll 600 patients at 140 sites globally.

Enrolled patients will receive atezolizumab at a fixed dose of 1200 mg administered intravenously on the first day of each cycle ([Figure 2](#)). One cycle of therapy will be defined as 21 days (\pm 5 days). Atezolizumab treatment will continue until investigator-assessed loss of clinical benefit, unacceptable toxicity, investigator or patient decision to withdraw from therapy, or death (whichever occurs first).

Figure 2 Study Schema

Chemo, standard systemic chemotherapy; CNS, central nervous system; ECOG PS, Eastern Cooperative Oncology Group performance status; FFPE, formalin-fixed paraffin-embedded; IV, intravenous; L, line; NSCLC, non-small cell lung cancer; RBR, Research Biosample Repository; TKI, tyrosine kinase inhibitor.

- a. Patients with a previously detected sensitizing EGFR mutation or ALK fusion oncogene must have received targeted TKI therapy (no restrictions on number or sequence) followed by at least one line of standard systemic chemotherapy prior to receiving atezolizumab. Patients will also be eligible if they discontinued first-line or second-line therapy due to intolerance.
- b. Response will be assessed by the investigator using RECIST v1.1 (see [Appendix 2](#)) and modified RECIST (see [Appendix 3](#)). Patients who continue atezolizumab treatment beyond radiographic disease progression assessed per RECIST v1.1 will be monitored with a follow-up scan at the next scheduled tumor assessment when the scan frequency is every 6 weeks, and will be assessed by modified RECIST criteria (see [Appendix 3](#)) until treatment discontinuation. If the scan frequency is every 9 weeks (see [Appendix 1](#)), a follow-up scan is recommended at 9 weeks or earlier if clinically indicated.
- c. In those patients for whom tumor assessments are performed as part of local clinical practice and are available for report after PD or atezolizumab treatment discontinuation, best overall response (BOR) and PFS will be assessed from the first date of the new anticancer therapy to the end of the study per RECIST v1.1 and modified RECIST.

The primary objective of the study is to evaluate the long-term safety of atezolizumab. Long-term safety will be assessed by monitoring the nature, severity, duration, frequency and timing of atezolizumab-related SAEs and atezolizumab-related irAEs. An irAE is defined as any adverse event of special interest (AESI) associated with systemic corticosteroid use within 30 days of the onset date. All-causality AEs, all-causality SAEs, AEs and SAEs leading to atezolizumab interruption or discontinuation, and AESIs will also be reported, as well as causes of death, vital signs, physical findings and clinical laboratory results.

Secondary objectives will assess the efficacy of atezolizumab. The main efficacy objective will be to evaluate the OS rate 2 years after the first dose of atezolizumab.

Other efficacy objectives will include evaluation of OS, OS rate at 3 years, PFS, ORR, and DOR (additional efficacy assessments may occur on an exploratory basis). All antitumor response assessments will be based on RECIST v1.1 and modified RECIST.

Exploratory objectives will include evaluation of the safety and efficacy of atezolizumab in patient subgroups differentiated by: presence or absence of CNS metastases at baseline; ECOG performance status; histological subtype; history of or current autoimmune disease; and prior anticancer treatment. Other exploratory and PRO outcomes will include objective response rate and progression-free survival 2 (PFS2) following start of new anticancer therapy, HR QoL as measured on the EORTC LQ-LC13, health utility score as measured on the EQ-5D-5L instrument, and expression of PD-L1 protein and cancer-related genes in tumor samples obtained before treatment. Finally, exploratory biomarkers may be assessed in tissue to assist in the potential development of new diagnostic assays and to assess biomarkers in terms of prognosis, response/resistance and safety.

Following discontinuation of study treatment, safety assessments will be conducted for 30 days after the last study drug administration or until initiation of other anti-cancer therapy (whichever occurs first). Thereafter, follow-up information on disease progression (unless this has already occurred), anti-cancer therapy and survival will be collected via telephone contact, patient medical records, and/or clinic visits approximately every 3 months until death, loss to follow-up, end of study (30 months after last patient in), patient withdrawal or study termination by the Sponsor, whichever occurs first. In addition, irAEs, SAEs and AESIs will be collected as described in Section [5.4.2](#).

In those patients for whom tumor assessments are performed as part of local clinical practice and are available for report after PD or atezolizumab treatment discontinuation, overall response rate (ORR) and progression-free survival (PFS) will be assessed from the first date of the new anticancer therapy to the end of the study. These data will be used in an exploratory fashion to assess whether prior atezolizumab treatment positively influences response to subsequent anticancer therapies.

An Independent Data Monitoring Committee (iDMC) will be established to review all AEs, irAEs, SAEs, AESIs and other cumulative safety data.

A Schedule of Assessments for this study is provided in [Appendix 1](#).

3.2 END OF STUDY AND LENGTH OF STUDY

The end of study and final analysis will occur when all enrolled patients have either died, withdrawn consent, are lost to follow up, or have been followed for 30 months since the last study patient is enrolled, whichever occurs first.

The primary analysis will occur approximately 6 months after the last patient has been enrolled.

The total length of the study, from screening of the first patient to the end of the study, is expected to be approximately 4 years.

3.3 RATIONALE FOR STUDY DESIGN

3.3.1 Rationale for Patient Population and Analysis Groups

Please refer to Section 1.3, Study Rationale and Benefit Risk Assessment.

3.3.2 Rationale for an Open-Label Single-Arm Design

The primary objective of this study is to assess the long-term safety profile of atezolizumab in a noncomparative fashion. Thus, as all patients are pre-specified to receive active treatment, the study will have an open-label and non-randomized design.

3.3.3 Rationale for Atezolizumab Dose and Schedule

The fixed dose of 1200 mg (equivalent to an average body weight-based dose of 15 mg/kg) was selected on the basis of both nonclinical studies and available clinical data from Study PCD4989g as described below.

The target exposure for atezolizumab was projected on the basis of nonclinical tissue distribution data in tumor-bearing mice, target-receptor occupancy in the tumor, the observed atezolizumab interim pharmacokinetics (PK) in humans, and other factors. The target trough concentration (C_{trough}) was projected to be 6 $\mu\text{g}/\text{mL}$ on the basis of several assumptions, including: 1) 95% tumor-receptor saturation is needed for efficacy, and 2) the tumor-interstitial concentration to plasma ratio is 0.30 based on tissue distribution data in tumor-bearing mice.

The atezolizumab dose is also informed by available clinical activity, safety, PK, and immunogenicity data. Anti-tumor activity has been observed across doses from 1 mg/kg to 20 mg/kg. The maximum tolerated dose of atezolizumab was not reached, and no dose-limiting toxicities have been observed at any dose in Study PCD4989g. Available preliminary PK data (0.03–20 mg/kg) from Study PCD4989g suggest that for doses ≥ 1 mg/kg, overall atezolizumab exhibits pharmacokinetics that are both linear and consistent with typical IgG1 antibodies.

Detectable anti-therapeutic antibodies (ATAs) were observed in patients at all dose levels but were associated with changes in PK for some patients in only the lower dose cohorts (0.3, 1, and 3 mg/kg). It is unclear from currently available data in these lower dose cohorts if administration of higher doses to patients with both detectable ATAs and reduced exposure would necessarily restore exposure to expected levels. No clear relationship between the development of measurable ATAs and safety or efficacy has been observed. Available data suggest that the development of detectable ATAs does not appear to have a significant impact on the PK for doses from 10 to 20 mg/kg in most

patients. Correspondingly, patients dosed at the 10-, 15-, and 20-mg/kg dose levels have maintained target trough levels of drug despite the detection of ATAs.

Currently available PK and ATA data suggest that the 15-mg/kg atezolizumab q3w regimen (or fixed-dose equivalent) for Phase II and Phase III studies would be sufficient to both maintain $C_{trough} \geq 6 \mu\text{g/mL}$ and further safeguard against both interpatient variability and the potential effect of ATAs that could lead to subtherapeutic levels of atezolizumab relative to the 10-mg/kg atezolizumab q3w regimen (or fixed-dose equivalent). From inspection of available observed C_{trough} data, moving further to the 20-mg/kg atezolizumab q3w regimen does not appear to be warranted to maintain targeted C_{trough} levels relative to the proposed 15-mg/kg atezolizumab q3w level.

Simulations do not suggest any clinically meaningful differences in exposure following a fixed dose or a dose adjusted for weight. On the basis of this analysis, a fixed dose of 1200 mg has been selected (equivalent to an average body weight-based dose of 15 mg/kg).

Selection of an every-21-day dosing interval is supported by this preliminary PK evaluation and allows for a convenient integration with common chemotherapeutic regimens.

3.3.4 Rationale for Biomarker Assessments

PD-L1 expression on tumor cells (TC) and immune cells (IC) varies significantly among patients with NSCLC, and these differing levels of PD-L1 expression have been shown to correlate with atezolizumab response in several studies (76, 79, 80, 87). Further defining the relationship between atezolizumab treatment outcomes in NSCLC and PD-L1 expression continues to be important, as it will advance the understanding of a potential differential benefit from atezolizumab treatment across PD-L1-defined patient subgroups, as well as add to the understanding of the basic biology underlying immune checkpoints and their role in cancer.

Therefore, to address these issues, the current study will collect, if available, tumor tissue obtained at the time of diagnosis (archival tissue) or at any time before the start of atezolizumab therapy and analyze PD-L1 expression by immunohistochemistry (IHC). As PD-L1 IHC is also tested routinely, results from local PD-L1 analysis will be collected instead of central testing or in addition to central testing. Results from the IHC assay will be used to correlate baseline levels of PD-L1 with subsequent safety and efficacy outcomes. If tissue quantity allows, other PD-L1 tests may be conducted to, e.g., assess concordance of methods (the pretreatment sample may also be used for other exploratory biomarker analyses [see next paragraph]).

For patients who received prior PD-1-targeted therapy, results from local PD-L1 testing should be provided, and whenever feasible, archival tissue obtained before the start of PD-1 therapy should be submitted for central IHC analysis. In order to better understand

the effect of anti-PD-1 therapy on PD-L1 expression, as well as its effects on anti-PD-L1 treatment efficacy, a biopsy should be taken prior to receiving atezolizumab therapy (screening biopsy).

NSCLC is a heterogeneous disease involving multiple genetic lesions and alterations in expression patterns (88-90). Therefore, in addition to PD-L1, other biomarkers may be examined in this study on an exploratory basis. This will be accomplished by, e.g., IHC and/or a variety of protein-, DNA- and RNA-based profiling methodologies. These analyses are of significant interest for their potential of revealing molecular mechanisms involved in advanced NSCLC carcinogenesis and susceptibility to atezolizumab treatment.

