1.2.1.4 OAK

OAK is a phase III study of atezolizumab monotherapy versus docetaxel in 1225 patients with locally-advanced or metastatic NSCLC. Eligible patients had relapsed disease that was progressing after 1–2 prior lines of chemotherapy (including at least 1 platinum-based regimen) and were allowed to have any PD-L1 expression status. OAK has two co-primary endpoints: OS in the ITT population; and OS in the TC1/2/3 or IC1/2/3 subgroup ($\geq 1\%$ PD-L1 expression). The primary outcome analysis (n=850 patients), which was sufficiently powered to test both co-primary endpoints, was presented at the 2016 meeting of the European Society for Medical Oncology (83).

At baseline, the atezolizumab (n=425) and the docetaxel (n=425) treatment groups had similar histology distributions, performance statuses, prior therapy rate, tobacco use, CNS metastasis rates, and EGFR-mutation statuses.

In all patients (ITT population), the median OS was 13.8 months (95% CI, 11.8–15.7 months) in the atezolizumab group versus 9.6 months (95% CI, 8.6–11.2 months) in the docetaxel group, indicating a significant treatment effect in favor of atezolizumab (HR, 0.73; p=0.0003). One-year survival rates were 55% and 41% in the atezolizumab and docetaxel groups of the ITT population, respectively, whereas the 18-month survival rates were 40% and 27% in the two treatment groups.

In the TC1/2/3 or IC1/2/3 subgroup ($\geq 1\%$ PD-L1 expression), which comprised 55% of enrolled patients, the median OS was 15.7 months (95% CI, 12.6–18.0 months) in the atezolizumab group versus 10.3 months (95% CI, 8.8–12.0 months) in the docetaxel group, again indicating a significant treatment effect in favor of atezolizumab (HR, 0.74; p=0.0102). Median OS positively correlated with PD-L1 expression status. Sixteen percent of patients were classified as TC3 or IC3; 31% were classified as TC2/3 or IC2/3; 55% were classified as TC1/2/3 or IC1/2/3; and 45% were classified as TC0 and IC0. Median OS in these subgroups were 20.5 months, 16.3 months, 15.7 months, and 12.6 months, respectively.

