- If available, pre-treatment FFPE tumor tissue (most recent sample) for PD-L1 testing and exploratory biomarkers. Most recent archival sample or a sample obtained during screening should be submitted if available (1 FFPE tissue block or 5–10 slides)
- For patients who have already been tested for PD-L1 by IHC, results and assay name are to be submitted
- For patients who were treated with anti-PD-1 therapy, sites are highly encouraged to submit the following samples if available:
- Archival tissue taken prior to treatment with PD-1 targeting agents (FFPE tissue block or 5–10 slides)
- Screening biopsy taken prior to treatment with atezolizumab (after PD-1 targeting agents (FFPE tissue block or 5–10 slides)

For sampling procedures, storage conditions, and shipment instructions, see the laboratory manual.

Exploratory biomarker research may include, but will not be limited to, the following analyses:

- PD-L1 IHC assessment
- Tumor DNA isolation for detection of gene alterations
- Tumor RNA isolation for gene expression profiling

Unless the patient gives specific consent for his or her leftover or unused samples to be stored for optional exploratory research (see Section 4.5.10.6), biological samples will be destroyed no later than the time of completion of the final Clinical Study Report, with the following exception:

- Leftover tumor tissue that remains after a maximum of 10 slides have been cut will be returned to the study site

When a patient withdraws from the study, samples collected prior to the date of withdrawal may still be analyzed, unless the patient specifically requests that the samples be destroyed or local laws require destruction of the samples.

Data arising from sample analysis, will be subject to the confidentiality standards described in Section 8.4.

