3.1.3 Biomarker Evaluable Population (BEP)

Patients from the safety population with at least one result for PD-L1 expression on tumor cells (TC) in either central or local assessments available. In case both central and local assessments are available, central assessments should be used.

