3.4.4 Subgroup Analyses

The OAK-LIKE Subgroup is defined as patients with the next characteristics:

- ECOG Performance status of 2: no
- Patients with previous anti-PD-1, anti-PD-L1, or ant-CTLA-4 therapy: no
- Presence of untreated CNS metastases at baseline: no
- Renal impairment (creatinine clearance < 30 mL/min (CKD-EPI)): no
- Liver
 - AST and ALT ≤ 2.5 times the upper limit of normal (ULN), with alkaline phosphatase ≤ 2.5 ULN OR
 - AST and ALT ≤ 1.5 x ULN, with alkaline phosphatase > 2.5 x ULN
- HIV-positive: no
- HBV/HVC status: not active

- History of autoimmune disease: no
- Concomitant steroid treatment ongoing at baseline: no

OS and PFS results across subgroups will be examined in the following subgroups. Subgroups with ≤ 10 patients will not be included.

- OAK-LIKE
- Demographics:
 - Age (<, \geq 65 years),
 - Sex,
 - Region (EMEA, Asia, LATAM),
 - Smoking status (never, current/previous)
- Baseline disease characteristics:
 - Histologic subtype (squamous, non-squamous),
 - ECOG performance status at baseline (0/1, 2),
 - Brain metastases at baseline (yes, no)
 - Liver metastases at baseline (yes, no),
 - History of autoimmune disease (yes, no),
 - Prior anti-PD-1 therapies (yes, no),
 - Renal impairment (eGFR<, \geq 60 mL/min/m²),
 - EGFR positive at baseline (yes, no),
 - ALK positive at baseline (yes, no),
 - Active hepatitis B or C at baseline (positive, negative),
- PD-L1 status (Central):
 - PD-L1 Expression on TC (<1%, \geq 1%, [1-50[%], \geq 50%)
- PD-L1 status (Local):
 - PD-L1 Expression on TC (<1%, \geq 1%, [1-50[%], \geq 50%)
- PD-L1 (BEP):
 - PD-L1 Expression on TC (<1%, \geq 1%, [1-50[%], \geq 50%)
 - Yes vs No
- PD-L1 (OAK-LIKE/BEP):
 - PD-L1 Expression on TC (<1%, \geq 1%, [1-50[%], \geq 50%)
 - Yes vs No

Summaries of OS and PFS, including Kaplan-Meier estimates of median OS and PFS, OS rate at 6, 12, 24 and 36 months, PFS rate at 6, 12 and 24 months will be produced separately for each level of the subgroup. For the primary analysis, only the rate at 6 and 12 months will be estimated.

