3.5.7 Subgroup Analyses

Safety summary tables and summary of AE by SOC/PT will be repeated for the following subgroups:

- OAK-LIKE Population
- Demographics:
 - Age (<, ≥ 65 years),
 - Age (<, ≥ 80 years),
 - Region (Europe, Asia, LATAM)
- Baseline disease characteristics:
 - Histologic subtype (squamous, non-squamous),
 - ECOG performance status at baseline (0/1, 2),
 - Brain metastases at baseline (yes, no)
 - Liver metastases at baseline (yes, no),
 - History of autoimmune disease (yes, no),
 - Prior anti-PD-1 therapy (yes, no),
 - Renal impairment (eGFR $<$, ≥ 60 mL/min/m²),
 - EGFR positive at baseline (yes, no),
 - ALK positive at baseline (yes, no),
 - Active hepatitis B or C at baseline (positive, negative),

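### Safety by PD-L1 expression is a listed exploratory endpoint, but the SAP's safety subgroups omit PD-L1; its rule for choosing a PD-L1 result also ignores sample date, which matters after prior anti-PD-1 therapy

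*Protocol*

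**What the plan says.** **The endpoint.** Protocol Section 3.3.4 opens by noting that "PD-L1 expression on tumor cells (TC) and immune cells (IC) varies significantly among patients with NSCLC" and later states: "Results from the IHC assay will be used to correlate baseline levels of PD-L1 with subsequent safety and efficacy outcomes". Section 1.3 says the same in other words. Table 9 (Section 2) lists safety as well as efficacy in subgroups by PD-L1 expression among the exploratory biomarker endpoints. SAP Section 2.2 refers to SAP Appendix 1 for the outcome measures, and that appendix repeats the endpoint.

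**The planned analyses.** SAP Section 3 opens by saying that the SAP's analyses take precedence over the protocol's. Section 3.4.4 examines OS and PFS in four PD-L1 blocks (Central, Local, BEP, OAK-LIKE/BEP), each headed "PD-L1 Expression on TC" with cuts at 1% and 50%. Section 3.5.7 introduces its list with "Safety summary tables and summary of AE by SOC/PT will be repeated for the following subgroups". PD-L1 is not in that list.

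**The choice of PD-L1 result.** SAP Section 3.1.3 defines the BEP as "Patients from the safety population with at least one result for PD-L1 expression on tumor cells (TC) in either central or local assessments available" and adds: "In case both central and local assessments are available, central assessments should be used". It sets no condition on when the tissue was collected. For patients with prior anti-PD-1 therapy, Protocol Section 4.5.7 encourages sites to send central laboratories two tissues if available: "Archival tissue taken prior to treatment with PD-1 targeting agents", and a screening biopsy taken after those agents. Section 3.3.4 also asks for local results in these patients and does not say which tissue they come from.

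**The concern.** Safety is this study's primary objective, and PD-L1 is its leading exploratory biomarker. A programmer working from the SAP would produce OS and PFS by PD-L1 and no adverse event tables by PD-L1. A stated endpoint would then go unanswered, or would be added later without a prespecified grouping.

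The second point concerns what the PD-L1 value describes. Patients with prior anti-PD-1 therapy are among those newly admitted to this study, and Protocol Section 3.3.4 asks for a biopsy after that therapy because it wants to learn how the therapy affects PD-L1 expression. If the BEP value comes from tissue taken before that therapy, it may not describe the tumor at the start of atezolizumab.

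**Working it through.** No stated design figure is in dispute, so the check is a comparison of the texts.

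**Safety by PD-L1**

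1. Endpoint: present in Protocol Table 9, Protocol Sections 1.3 and 3.3.4, and SAP Appendix 1. The appendix reproduces the version 3 synopsis. The version 6 protocol keeps the same endpoint, so it was not withdrawn in between.
2. Efficacy subgroups (SAP 3.4.4): four PD-L1 blocks.
3. Safety subgroups (SAP 3.5.7): OAK-LIKE (1), two age splits and region (3), and ten baseline disease characteristics (histology, ECOG, brain metastases, liver metastases, autoimmune disease, prior anti-PD-1, renal impairment, EGFR, ALK, hepatitis). That makes 1 + 3 + 10 = 14 entries, of which none is PD-L1.
4. Precedence: the SAP governs, so the protocol's undertaking does not fill the gap.
5. Feasibility: the BEP is drawn from the safety population, so the denominators for adverse event tables by PD-L1 already exist.

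**Choice of sample**

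1. Patients without prior anti-PD-1 therapy: Protocol 4.5.7 asks for the most recent sample, so the problem of tissue predating anti-PD-1 therapy cannot arise.
2. Patients with prior anti-PD-1 therapy: pre-therapy archival tissue goes to central testing where feasible, and a post-therapy biopsy may also be sent.
3. If the archival tissue has a central read and the later tissue has only a local one, SAP 3.1.3 selects the archival read. If both have central reads, Section 3.1.3 does not say which to use.
4. Reach of the central-over-local rule: only the BEP rows. The Local block is reported separately, and OAK-LIKE excludes patients with prior anti-PD-1 therapy, so the OAK-LIKE/BEP rows are unaffected.
5. Number affected: the documents give neither the number of patients with prior anti-PD-1 therapy nor which of their samples were tested, so no count can be derived.

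**The case against.** **On safety.** SAP Section 2.2 adopts the Appendix 1 endpoints, so one can argue that the analysis is unspecified rather than dropped. The protocol's own subgroup list in Section 6.6.3 also omits PD-L1. The first point is fair as to intent, but Section 3.5.7 is an explicit list, and following it yields no PD-L1 safety table. Section 6.6.3 is a list for exploratory efficacy analyses that might be repeated, so it does not settle the safety question.

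**On sample choice.** The override needs a particular pattern of testing. Both tissues may have central reads, and no text says that local results come from the screening biopsy. SAP Section 3.3 defines baseline as the last available value recorded by first dose, which could be read as selecting the later of two central results. This stands as a limit: the outcome is possible, not certain. The baseline rule does not close the gap, because it turns on when a value was recorded rather than when tissue was taken, and it is not tied to the BEP rule. Tissue is shipped only once a patient is found eligible (Protocol Appendix 1), so a central result could arrive after first dose.

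**A stronger reading to resist.** Because the protocol's rationale and the OAK summary use both cell types (in OAK, "45% were classified as TC0 and IC0"), a reader might infer that a patient negative on tumor cells and positive on immune cells falls in the wrong SAP group. The documents do not support this. The SAP rows are labelled as tumor-cell groups, and such a patient is correctly placed in them. Table 9 prescribes no combined scoring, nothing says immune cells will be scored in this study, and no PD-L1 comparison with OAK is planned. A loss in months of survival difference cannot be stated either: the share of patients positive on immune cells only is not given, and OAK's 45% doubly negative bounds it only between 0 and 55%.

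**Conclusion.** The safety gap holds on the text alone and needs no assumption: four PD-L1 blocks for OS and PFS, none for safety, against an endpoint that names both. The sample-date gap is real but secondary. It is a missing rule that may place an outdated PD-L1 value in the BEP rows for some patients with prior anti-PD-1 therapy, in a number the documents do not reveal. Both concern exploratory analyses in a single-arm descriptive study. The two primary incidence endpoints and the sample size are unaffected.

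**What to change.** 1. **SAP Section 3.5.7:** add the BEP tumor-cell PD-L1 groups already used in Section 3.4.4 to the safety subgroup list. The cost is a few extra descriptive tables and no new data.
2. **SAP Section 3.1.3:** for patients with prior anti-PD-1 therapy only, use the PD-L1 result from the latest sample collected before the first atezolizumab dose, preferring central to local for that sample. Leave the present rule for everyone else. The downside is somewhat more mixing of assays among these patients. The local assay name is already requested (Protocol Sections 4.5.2 and 4.5.7), so it can be shown.
3. **Optional:** add rows combining tumor-cell and immune-cell scores, only if immune cells were scored.
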